- Screening follow up. We will train the outreach team how to conduct all of the guideline appropriate follow up described in detail below, including follow up of patients with abnormal FITs.
- Screening tracking database. Will train the outreach team how to take full advantage of the tracking database, which can generate lists of patients requiring follow up (e.g. patients due for phone reminders to complete screening), document patient interactions (e.g. delivery of phone reminders or documentation of triage for colonoscopy for patients with abnormal tests), and document screening outcomes (e.g. FIT test completion, FIT results, and colonoscopy results for patients with abnormal tests).
- **Program management**. We will work with the team to learn how to set daily, weekly, and monthly goals for the screening program. For example, each cohort of patients invited to complete screening through a given year has a timeline of events that must occur over a two month period that includes invitation delivery, phone reminder delivery within 2 to 3 weeks post invitation, and follow up of abnormal tests (described in detail below). [name] has extensive experience with management of other disease management programs, and in developing and implementing quality improvement initiatives at JPS. Through his work as a family physician and endoscopist, [name] has extensive experience in leading medical care teams. Thus, the physician champions of the program at JPS have the expertise and experience necessary to take on primary program management responsibilities.

Approach to Screening Invitation and Promotion

All patients meeting inclusion/exclusion criteria will receive mailed invitation to complete screening, with processes to promote screening completion. The list of eligible patients will be divided into multiple groups so that the expected group of 20,000 patients will receive invitations spread out in time, so as to avoid overwhelming the system. All screening processes were included in our prior CPRIT sponsored outreach program, and therefore are already developed and ready for use. The specific components of outreach include:

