The incentive will consist of either a \$5 or \$10 gift card to a local retailer that will be sent to the patient upon return of an FIT kit. Incentives will be mailed by the JPS outreach team, in exchange for successful FIT completion, after the FIT has been returned. \$5 and \$10 incentives were chosen for several reasons. First, these levels of incentives, if shown effective, could be potentially sustained by the JPS system beyond the timeframe of the grant. Higher incentives, while potentially more powerful in inducing participation, would be unsustainable and therefore do not merit study at this time. Comparing \$5 and \$10 incentives is important because if offering incentives is effective in boosting screening, it is important to know the minimum incentive required for meaningful changes in participation. Incentives are to be offered to all patients who are assigned to the incentive strategy. We considered, but rejected, restricting incentives to only patients who initially do not respond to screening invitations. This was because restricting incentives to non-responders would logistically complicate outreach activities. It is important to note that patients meeting study inclusion criteria must have a minimum of 1 visit to a JPS Primary Care clinic within the last year. Considering these patients have an established baseline relationship with the JPS primary care system, the addition of a modest financial incentive should not create undue influence in patients that otherwise would still have exposure to information on the benefit of screening. Since participation in this standard of care screening poses minimal to no risk, the chances that incentives may motivate research participants to take unnecessary risks are low.

Screening Completion Follow Up. Follow up for determining screening completion for all included patients will be through the end of Year 3 regardless of whether or not patients respond to screening invitations. As is explained below, screening rates will be measured for all patients included for outreach invitations. For patients who die on follow up or who do not have additional health system encounters, follow up will be censored at time of death or last health encounter, respectively.

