Data Sources and Data Tracking. *Our approaches to data acquisition, as well as data tracking have been previously developed and previously used to evaluate CRC screening rates and deliver screening.* The primary data source used to identify patients eligible for our outreach program will be JPS administrative claims database and Epic electronic medical record. At baseline, these data will be queried to identify all 50 to 64 year old patients potentially eligible for program inclusion. Demographic data, such as sex and race/ethnicity, as well as visit data, such as dates of any health system visits and any associated CPT codes with health system visits will be extracted and analyzed to determine which patients are eligible and up-to-date with screening. Data required for inviting patients to screening and tracking follow up, such as names and addresses, will be imported into a tracking database that has been previously developed and tested for this purpose. The tracking database facilitates all day to day program activities and associated data collection. For example, daily, a report is generated of patients who have been mailed FIT, and are due for follow up phone reminders to complete the FIT and return it. The database also allows for updating patient results, such as results of FIT and colonoscopy tests.

Sub-Study Procedures:

A sub-study will be conducted with the goal of identifying strategies that may further increase rates of 1) initial participation in colorectal cancer screening, and 2) follow up of abnormal colorectal cancer screening tests with colonoscopy. This sub-study involves 2 parts:

Part 1) Participants scheduled to receive mailed fecal immunochemical test (FIT) outreach for the first time late in the 2nd year of the study (currently ongoing) will be randomly assigned to receive one of three invitation letters, which vary slightly from one another. These letters represent small, but potentially impactful modifications to our original invitation letters.

All participants randomized to the original \$5 and \$10 incentive groups were enrolled during Year 1 of the study. After the incentive groups reached full enrollment, all new participants received the Version 8, June 29, 2015 11

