standard (non-incentive) invitation only. For the sub-study, the standard invitation letter will be replaced with one of the 3 modified letters. All new participants will be randomized to receive one of the 3 letters during 2 predetermined rounds of invitations (involving n=2,124 individuals).

Rationale and plan for sub-study part 1: Over nearly 2 years of our prevention program, we have tested a systematic screening outreach strategy for increasing screening completion among uninsured patients, not up to date with screening. Through these carefully evaluated interventions, we have shown that our outreach invitation strategy, particularly when it includes FIT invitations, markedly increases screening completion among the uninsured. Indeed 36% of individuals invited to complete FIT return the test. While this rate of participation is substantial, it may be improved by making changes to our invitation letters. In 2 predetermined rounds of invitations (involving n=2,124 individuals), we will slightly modify the invitation letters to test our hypothesis that providing information in the letter about the value of the kit and attenuating concern about future cost will further increase FIT and follow-up response rates.

There will be 3 conditions for the invitation letter and individuals will be randomly assigned 1:1:1 to each condition. The 3 conditions contain just slight differences in the information provided in the letter, as follows: (i) a control invitation letter (similar to letters in previous studies with some slight wording and grammatical improvements, (ii) the control letter plus the addition of one line informing recipients of the average value of the procedure (~\$200), and (iii) a letter with the average value and a sentence assuring patients that should a follow-up test be requested, it will be provided free of charge.

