Additional patients will be assessed for inclusion/exclusion criteria annually in Years 2 and 3 of the program. Each year, patients who newly meet our inclusion/exclusion criteria will be included in the program. For example, patients newly turning 50 in year 2 or 3 meeting all other inclusion/exclusion criteria will receive screening outreach. Similarly, a 60 year old patient new to the JPS system and meeting inclusion/exclusion criteria will also receive screening outreach. We think this approach reflects the ideal implementation of a standing CRC outreach program.

Sources of Research Material:

There are several sources of research material for this project:

- Administrative and electronic medical record databases at JPS. These data systems will be used to identify patients meeting inclusion/exclusion criteria, and to record outcomes of screening invitation.
- **Results of fecal immunochemical tests (FIT).** Patients will be invited to complete screening with a one-sample FIT. These kits will be processed by the JPS clinical lab, and the results will be recorded in the electronic medical record. Results of testing, including whether the test was abnormal or normal, and the level of hemoglobin present in the sample, will be collected
- **JPS cancer registry**. This resource will be accessed to identify patients enrolled in the screening program who develop CRC during the follow up time frame.
- **Study tracking database**. This database will record in real-time delivery of all screening interventions, and outcomes of the interventions. In addition, process variables, such as time spent on phone with patients, failed mailings due to wrong address will be collected. The study tracking database has been created for exclusive use by screening program personnel.
- Interviews of JPS personnel who will be conducting outreach interventions. The purpose of these interviews will be to understand the challenges to implementation of the outreach program within the health system.

Variable	Justification	Source
Baseline characteristics and elig	gibility criteria	
first name, last name	Required for delivery of	JPS administrative and
	screening invitations	electronic medical record
date of birth	Required for eligibility criteria	databases
Sex	Screening rates can differ by	
	sex	
Race/ethnicity	Screening rates may differ by	
	race/ethnicity	
Primary language	Use to identify preferred	
	language for study interventions	
Home address	Required for screening	

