we will even have 90% power to detect a smaller screening rate increase of \geq 5% (Power was computed with nQuery Advisor Software v.7.0).

Evaluation Aim B) Compare rates of initial and repeat screening completion among 1) Patients offered a modest financial incentive to complete screening, in addition to outreach invitations (n=2,000), vs. 2) Patients offered outreach invitations alone (n=~18,000). The rate of initial screening completion will be defined by:

Initial	# patients completing a FIT
Screening	Year 1
Completion Rate =	# of patients sent FIT invitation Year 1

We will compare the initial screening completion rate for patients offered the financial incentive, in addition to screening outreach, to the initial rate for patients offered screening outreach alone using a Chi-square test of proportions, with a 2-sided p value <0.05

considered statistically significant. The rate of repeat screening for Years 2 and 3 will be defined by:

Year 2	# patients completing FIT	Year 3 Repeat	# patients completing FIT
Repeat	screening Year 2	Completion	screening Year 3
Completion	# patients completing FIT Year 1	Rate =	# patients completing FIT Year 2
Rate =	with normal result		with normal result

We will compare initial FIT completion rates for the financial incentive plus organized outreach vs. organized outreach alone groups using a Chi-square test, with a 2-sided p value <0.05 considered statistically significant. The same approach will be taken for comparing repeat FIT completion rates for Years 2 and 3.

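### The Aim B initial completion rate does not define Year 1 or set a window from each patient's own mailing; read as the study year, it can lose more late returns in the control group than in the incentive group

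*Combined protocol and SAP*

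**What the plan says.** The Aim B formula for initial completion puts "patients completing a FIT" in Year 1 over the number "of patients sent FIT invitation Year 1". The Year 2 repeat rate has as its denominator the patients who completed a FIT in Year 1 with a normal result. Neither formula refers to the date on which a patient was mailed.

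Four other parts of the document bear on this:

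- **Staggering.** Under Approach to Screening Invitation and Promotion, patients "will receive invitations spread out in time, so as to avoid overwhelming the system".
- **Allocation over time.** Under Sub-Study Procedures, the "incentive groups were enrolled during Year 1 of the study". The text continues: "After the incentive groups reached full enrollment, all new participants received the" "standard (non-incentive) invitation only".
- **Use of the word Year.** The sentence on incentive enrolment uses it for a study year. The section on exclusion criteria, which also covers new entrants, assesses additional patients "annually in Years 2 and 3 of the program".
- **Follow-up.** Under Screening Completion Follow Up: "Follow up for determining screening completion for all included patients will be through the end of Year 3". The Aim B formula does not use that horizon.

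**The concern.** If Year 1 is the study year, observation time depends on when a patient happened to be mailed. Someone mailed in week 2 has about 50 weeks to be counted. Someone mailed in week 50 has two, and has barely reached the point at which live reminder calls are due (2 to 3 weeks after invitation). A kit that this second patient returns in Year 2 is missing from the Year 1 numerator, and the patient is also missing from the Year 2 repeat denominator.

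That understates completion in any arm mailed late. It biases the comparison only if the arms were mailed on different schedules. The documents make this possible: once the incentive groups were full, any remaining Year 1 invitees were controls only, and these are the patients with the least time to respond. A shortfall among them would look like an incentive effect. Aim B is declared positive at a two-sided p below 0.05 with large groups, so a difference of a few points is enough to matter.

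**Working it through.** **The plan's own figure.** Aim B claims over 90% power for a 5-point difference with 2,000 vs 18,000 at two-sided 5%. At 33% vs 38% the pooled rate is 33.5%. The null SE is √[0.335×0.665×(1/2,000+1/18,000)] = 0.01113, and the alternative SE is √(0.38×0.62/2,000 + 0.33×0.67/18,000) = 0.01141. Then (0.05 − 1.96×0.01113)/0.01141 = 2.47, so power is 99.3%. The stated figure is sound.

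**Inputs to the check.**
- From the documents: 33% completion (prior program's FIT arm) and 2,000 incentive patients.
- Assumed number of Year 1 controls: 10,319 − 2,000 = 8,319, taking Table 1's count of patients not up to date as a stand-in for Year 1 invitees.
- Assumed, with no support in the documents either way: no true incentive effect; mailing uniform from week 0 to week H; exponential return delay with mean m of 2, 4 or 6 weeks among those who return; returns counted only up to week 52; incentive mailing over the first 26 weeks.

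**Formula.** Counted rate = 0.33 × {1 − (m/H) × [e^(−(52−H)/m) − e^(−52/m)]}.

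**Example, m = 4.** Incentive arm, H = 26: 0.33 × (1 − 0.1538×0.0015) = 32.99%. Controls, H = 52: 0.33 × (1 − 0.0769) = 30.46%. Difference 2.53 points. With controls stopped at week 48: 0.33 × (1 − 0.0833×0.368) = 31.99%, difference 1.00. With controls stopped at week 44: 0.33 × (1 − 0.0909×0.135) = 32.59%, difference 0.40.

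**False-positive rate**, from the pooled two-proportion test. For m = 6 and controls to week 52, the difference is 3.71 points, the null SE 1.140 points and the alternative SE 1.163 points. (1.96×1.140 − 3.71)/1.163 = −1.27, so the test rejects in about 90% of trials.

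Spurious difference in points, with the share of trials significant at 5%:

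| Control mailing ends | m = 2 weeks | m = 4 weeks | m = 6 weeks |
|---|---|---|---|
| Week 52 | 1.3 (20%) | 2.5 (59%) | 3.7 (90%) |
| Week 48 | 0.2 (5%) | 1.0 (14%) | 2.0 (42%) |
| Week 44 | 0.03 (5%) | 0.4 (6%) | 1.1 (16%) |
| Same schedule in both arms | 0 (5%) | 0 (5%) | 0 (5%) |

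If the incentive groups filled at month 9 instead, with control mailing to week 52, the differences are 1.3, 2.4 and 3.2 points. So the end of control mailing matters more than how early the incentive groups filled. On a shared schedule running to week 52 there is no bias between arms, but both read 31.7%, 30.5% or 29.2% instead of 33%.

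**The case against.** A reader might infer that the plan imposes a calendar cut-off. It does not say so. Year 1 could mean the first invitation cycle: the program-management text describes a two-month sequence of events for each cohort invited through a given year. Aim B also counts all of the roughly 18,000 non-incentive patients as its comparator, although people first invited in Years 2 and 3 could not enter a study-year denominator. The study-year reading rests on how the word is used elsewhere. This objection stands, and it is why the point is conditional.

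A reader might also infer that late invitees are lost to follow-up. They are not. Screening completion is ascertained to the end of Year 3, so a late return is recorded; under the study-year reading the formula simply does not count it.

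The strongest inference would be that Aim B is biased towards incentives. The documents do not establish that. They give neither the date on which the incentive groups filled nor a mailing schedule, and the later standard-letter invitees may have been mainly Year 2 entrants. The largest differences need control mailing up to the last weeks of Year 1. Even 3.7 points is below the 5-point difference used for power and the 10-point difference that the plan calls clinically meaningful.

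What the objection does not remove is that the outcome is undefined on a point that can change the p-value, and that no reading of Year 1 is stated.

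**Conclusion.** The definition should be repaired. The formula names no window and leaves Year 1 undefined. Under the reading most consistent with usage elsewhere in the document, it counts late returns as failures and also drops those patients from the Year 2 repeat denominator. Bias in favour of incentives follows only if, in addition, the incentive groups filled before Year 1 control mailing ended.

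Under the assumptions above the size runs from zero (shared schedule) to 3.7 points (6-week mean delay, control mailing to year-end), and most of the range disappears if the last control round went out 8 weeks before year-end. Slower returns than assumed would raise these figures. The power statement for Aim B is not in error. The $5 vs $10 comparison in Aim C uses the same definition but should be largely unaffected if the two incentive groups were mailed concurrently.

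**What to change.** Define initial completion as FIT return within one fixed interval from each patient's own mailing date, the same in both arms. Twelve months would match the window of the prior program's 33% (Table 2). Define the Year 2 and Year 3 repeat rates in the same way from each repeat invitation. Because follow-up ends with Year 3, the interval for the last repeat round must fit before that date, so it may need to be shorter than 12 months. The dates needed are already held in the tracking database.

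The common window alone removes the truncation. As a further safeguard against controls invited at a different time, base the main incentive comparison on patients invited in rounds where incentive assignment was open, or stratify by invitation round. Report the date on which the incentive groups filled.

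The costs are modest. Restricting to open rounds leaves fewer controls. With an assumed 4,000, the null SE is 0.01303 and the alternative SE 0.01316 at 33% vs 38%, so (0.05 − 1.96×0.01303)/0.01316 = 1.86 and power is 96.8%. The protocol is at Version 8 (June 2015) and already reports a 36% return rate, so the change needs a dated amendment that states the reason and whether results by arm had been seen.
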